2.2 Goal 2 Tolerability

Evaluate the tolerability of Scrambler therapy and compare it to TENS therapy, in this population.

Hypothesis 2: Scrambler therapy will be well tolerated and there will be no substantial differences in side effects between the Scrambler and TENS treatment groups.

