4.0 Test Schedule

Use for first treatment period; repeat for second treatment period

Tests and procedures	Active Monitoring Phase				
	≤30 days prior to registration	Day 1, Prior to therapy	Daily for 14 consecutive days beginning on Day 1 of active therapy	Last day of assigned therapy (±1 day)	Weekly for 8 weeks
History and exam, PS ¹ , Eligibility questions ² (Appendix II: A or B)	X				
Pregnancy test ³		X			
Declaration of most problematic site (upper versus lower extremities) and most problematic symptom (tingling versus pain): Appendix III	X				
Pain/tingling questionnaire regarding the prior week (Appendix IV: A or B)		X ⁴			
Patient Questionnaire: Before each treatment (Appendix V: A or B)		X ⁵	X ⁵		
Patient Questionnaire: After each treatment (Appendix VI: A or B)			X ⁵		
EORTC CIPN 20 (Appendix VII)		X		X ⁶	X
Patient Questionnaire: Analgesic Use (Appendix VIII)		X	X		X
Patient Questionnaire After each therapy and during weekly follow-up: Global Impression of Change and Patient Preference (Appendix IX: A or B)			X ⁷		X ⁷
Daily Treatment Log and Adverse Assessment (Appendix X)			X		
Individual Patient Dermatome Map-Electrode Placement (Appendix XI) Scrambler only			X		
Audiovisual recordings ^R			X ⁸		
Weekly follow-up patient questionnaire (Appendix XII:A or B)					X ⁹
Written patient summary (if the patient is willing to provide) ^R					X ¹⁰
Research Blood draw for CBC/diff and mRNA ^{11,R}		X		X	
fMRI ^{12,R}		X		X	
Quantitative Sensory Testing ^{13,R}		X		X	

Tests and procedures	Active Monitoring Phase				
	≤30 days prior to registration	Day 1, Prior to therapy	Daily for 14 consecutive days beginning on Day 1 of active therapy	Last day of assigned therapy (±1 day)	Weekly for 8 weeks
Study Coordinator/Nurse phone call to discuss therapy and any concerns, record any adverse events that are reported and to remind the patient to complete questionnaires and mail them			X ¹⁴		X

Footnotes:

1. PS must be done ≤7 days prior to registration.
 2. Appendix II A or B, as labeled depending on neuropathy area type. (This evaluation is used for eligibility.)
 3. For women of childbearing potential only. Must be done prior to first Scrambler therapy (or the first day of the second treatment period, if Scrambler therapy is crossover).
NOTE: This testing is not needed for TENS therapy.
 4. Appendix IV A or B, as labeled depending on neuropathy area to be treated

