 5. Beginning on Day 1 of active treatment and continuing for 14 consecutive days, complete Appendix V daily pre/post therapy. If no therapy is received on a day during this timeframe, complete once daily. To be filled out only for primarily treated area. For post-therapy questionnaires VIA and VIB.
 6. Prior to the last therapy.
 7. Appendix IX A or B, as labeled depending on pain or neuropathy area to be treated.
 8. If patient provides written consent for AV recording. Recording may be done on any day.
 9. Appendix XII A or B, as labeled depending on pain or neuropathy area to be treated.
 10. To be completed any time after completion of active treatment.
 11. Optional use in selected patients: Blood draws are completed at Baseline (prior to treatment) and on the last planned day or two of treatment (e.g., Day 9 or 10, if 10 treatments are given but sooner if earlier treatment completion is planned) (±2 days). Ideally, do prior to treatment. See [Section 14.0](#).
 12. fMRI: Optional use in selected patients, do at baseline and on approximately the last day of the initial treatment (±1 day).
 13. Quantitative sensory testing: Optional use in selected patients, do at baseline and then the last day of the initial treatment (±3 days) on 10 patients from each cohort. Do prior to treatment.
 14. For TENS patients only: Study Coordinator or Nurse to call on Treatment Day 2 and once on Treatment Day 8-10 to assess toxicities and remind the patient to complete daily questionnaires and mail them back.
- R Research funded

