7.12 Subsequent days of Scrambler Therapy

7.121 Treatment will be administered using the above outlined principles of the recommended scrambler for 30 minutes of application time, on up to 10 consecutive weekdays as long as the patient has numbness/pain/tingling rating of more than 0 at the time they come in for treatment. This is

because without pain, there is no guidance to the provider about electrode placement. Subsequent treatments can rapidly be titrated up to the highest intensity tolerated during the previous treatment. Up to three days may be skipped to allow for weekends and holidays, if needed. Treatment must start on a Monday, Tuesday, or Wednesday; with the goal being 3 consecutive days of treatment before break (e.g. treatment cannot start Wednesday before Thanksgiving holiday weekend). The total of 10 treatments must be scheduled to be able to be completed within 16 calendar days).

- 7.122 The electrode placement may be modified on subsequent days, depending on how a patient responds to treatment.

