10.2 Expedited Adverse Event Reporting Requirements

	Grade 4 or 5 Unexpected with Attribution of Possible, Probable, or Definite	Increased Incidence of an Expected AE ¹
FDA Form 3500 (MedWatch) within 10 working days ²	X	X

1. An increased incidence of an expected adverse event (AE) is based on the patients treated for this study at their site. A list of known/expected AEs is reported in the package insert or the literature, including AEs resulting from a drug overdose.
2. Submit form to the FDA, MedWatch, [name], by fax at [name] or online at <http://www.fda.gov/Safety/MedWatch/HowToReport/default.htm>.

Mayo Clinic Cancer Center (MCCC) Institutions: Attach copies to the Mayo Cancer Center SAE Reporting Form:

The MCCC Regulatory Affairs Unit (RAU) Risk Information Specialist will determine and complete IRB reporting. The RAU will submit to the MCCC SAE Coordinator.

- 10.3 Adverse events to be graded at each evaluation and pretreatment symptoms/conditions to be evaluated at baseline per the CTCAE v4.0 grading: NONE.
 - 10.31 Submit via appropriate MCCC Case Report Forms (i.e., paper or electronic, as applicable) the following AEs experienced by a patient and not specified in Section 10.3:
 - 10.311 Grade 2 AEs deemed *possibly, probably, or definitely* related to the study treatment or procedure.
 - 10.312 Grade 3 and 4 AEs regardless of attribution to the study treatment or procedure.
 - 10.313 Grade 5 AEs (Deaths)
 - 10.3131 Any death within 30 days of the patient's last study treatment or procedure regardless of attribution to the study treatment or procedure.
 - 10.3132 Any death more than 30 days after the patient's last study treatment or procedure that is felt to be at least possibly treatment related must also be submitted as a Grade 5 AE, with a CTCAE type and attribution assigned.

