11.2 Adverse Event Assessment

Adverse events will be evaluated by using CTCAE criteria based on patient reporting and nurse observation and/or assessment.

11.3 mRNA

mRNA results will be correlated with outcomes. See [Section 14.0](#).

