16.32 Secondary efficacy endpoints

Perceived treatment efficacy from the Subjective Global Impression of Change instrument (Appendix IXA and B) will be summarized (median and range for impression of change and frequency for preference) by arm and compared

(Wicoxon rank-sum test for impression of change and Chi-square test for preference) between treatment arms.

EORTC CIPN20 scores and changes in scores will be summarized (mean, sd, median, range) at each time point by arm and will be compared between arms using two-sample t-tests.

- 16.33 Goal: Evaluate the tolerability of Scrambler therapy and compare it to TENS therapy, in this population.

Frequency and type of toxicities occurred during therapy will be summarized by treatment arm and compared between arms using Fisher-exact test.

- 16.34 Goal: Evaluate whether Scrambler therapy, compared to TENS therapy, can decrease the use of pain medication for CIPN.

Type and frequency of analgesic used will be summarized by treatment arms and will be compared using Fisher-exact test.

- 16.35 Goal: Explore whether mRNA gene expression changes are similar to that previously reported by Starkweather et al.

In a descriptive manner, the gene expression will be compared to what was previously reported.

- 16.36 Goal: Explore whether Scrambler therapy will change fMRI.

Changes in fMRI following Scrambler therapy will be described in the subset of patients selected for this component of the study.

- 16.37 Descriptive statistics will be used for the data from Quantitative Sensory Testing.

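### The Goal 2 toxicity test covers an undefined treatment period in which adverse events are ascertained differently by arm, and omits the weekly calls scheduled alike in both arms

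*Combined protocol and SAP*

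**What the plan says.** Goal 2 (Section 2.2) is to compare tolerability, with the hypothesis that "there will be no substantial differences in side effects between the Scrambler and TENS treatment groups". Its only planned analysis is in Section 16.33: "Frequency and type of toxicities occurred during therapy will be summarized by treatment arm and compared between arms using Fisher-exact test". That sentence does not say how many days the period covers, which record supplies the events, or which grades count.

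**Scrambler arm.** Section 7.1 has an operator place the electrodes and set the intensity while talking to the patient. Sessions are given "on up to 10 consecutive weekdays as long as the patient has numbness/pain/tingling rating of more than 0 at the time they come in". Section 7.121 adds: "The total of 10 treatments must be scheduled to be able to be completed within 16 calendar days". Appendix XA is the daily log for this arm, with cable settings, scores before, during and after the session, and an adverse-effect line.

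**TENS arm.** Section 7.2 has the patient treat at home for 30 minutes a day for 14 days after a hands-on lesson. Appendix XB is the log, with a nearly identical adverse-effect line. Footnote 14 of the Section 4.0 schedule adds: "For TENS patients only: Study Coordinator or Nurse to call on Treatment Day 2 and once on Treatment Day 8-10 to assess toxicities".

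**Both arms.** Section 11.2 grades events "based on patient reporting and nurse observation and/or assessment". Section 4.0 puts the daily log in one 14-day column. It also schedules a weekly call for eight weeks to "record any adverse events that are reported", and that entry does not carry the TENS-only footnote. Section 18.12 requires the adverse-event form in Observation as well as during treatment.

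**The concern.** A between-arm test of event counts is interpretable only if events have the same chance of being found in each arm. Here they may not. Nurse observation is available at every Scrambler session but cannot take place while a patient uses TENS at home. Section 10.3 lists no adverse events to be graded at each evaluation, so nothing standardises what is asked, and capture depends on who asks and how often.

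Missed TENS events could create a difference that the devices did not cause. They could also hide a real excess on TENS, and a non-significant result would then look like support for the hypothesis of no substantial difference. The contacts that are scheduled identically, the eight weekly calls, are the ones that Section 16.33 leaves out.

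**Working it through.** The plan states no event rate, power or margin for this test, so there is no figure of its own to reproduce. Table 16.51 concerns the primary endpoint and does not bear on this point.

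**1. Scheduled contact (Sections 4.0, 7.1, 7.2)**

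| | Scrambler | TENS |
|---|---|---|
| Staff contact during treatment | up to 10 sessions in person | teaching session, then 2 toxicity calls |
| Written adverse-effect line | Appendix XA | Appendix XB |
| Treatment days | up to 10 | 14 |
| Treatment minutes | 10 × 30 = 300 | 14 × 30 = 420 |
| Weekly follow-up calls | 8 | 8 |

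The ratio of treatment minutes is 420/300 = 1.4.

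**2. Calendar length.** Scrambler must start on a Monday, Tuesday or Wednesday. Ten consecutive weekdays, counted in blocks of weekdays and weekends, span:
- Monday start: 5 + 2 + 5 = 12 days
- Tuesday start: 4 + 2 + 5 + 2 + 1 = 14 days
- Wednesday start: 3 + 2 + 5 + 2 + 2 = 14 days

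The limit with skipped days is 16, and TENS is 14. A Scrambler course may also end early if ratings reach zero; the documents do not say how often.

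**3. Effect of unequal capture (illustration with assumed rates).** Take 25 patients per arm (Section 16.5), a true risk p in both arms, full capture in Scrambler and a captured fraction c in TENS. The chance of a two-sided Fisher p ≤ 0.05 is the sum, over all pairs (i, j) that reach it, of Bin(i; 25, cp) × Bin(j; 25, p).

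| True risk, both arms | c = 100% | 75% | 50% | 25% |
|---|---|---|---|---|
| 10% | 0.9% | 0.9% | 1.3% | 2.1% |
| 20% | 2.2% | 3.5% | 8.6% | 19.8% |
| 40% | 3.0% | 7.0% | 23.1% | 59.1% |

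**4. Effect in the hiding direction.** If the true risk is 40% on TENS and 10% on Scrambler, the same sum gives a power of 59.1% with full TENS capture, 30.5% at c = 75% and 8.6% at c = 50%.

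**5. Effect of more treatment days.** With an equal risk h per treatment day, the share of patients with an event is 1 − (1 − h)^10 on Scrambler and 1 − (1 − h)^14 on TENS. For h = 1% this is 9.6% against 13.1%; for h = 2%, 18.3% against 24.6%. This pushes TENS counts up, while lower capture pushes them down.

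**6. Feasibility of matched questions.** From a Monday, Tuesday or Wednesday start, Day 2 is a Tuesday, Wednesday or Thursday. Days 8-10 run Monday to Wednesday, Tuesday to Thursday, or Wednesday to Friday. All are weekdays, so a Scrambler patient still in treatment normally has a session then.

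**The case against.** The strongest reply is that the plan already narrows the gap. The two TENS calls exist to assess toxicity, TENS patients may phone the nurse, and both logs prompt for adverse effects. Section 8.0 expects no substantial toxicity, and Section 10.31 requires routine submission only of Grade 2 events at least possibly related, Grade 3 and 4 events, and deaths. If Section 16.33 uses submitted events, the mild ones most sensitive to prompting largely drop out. The trial is also exploratory (Section 16.5), and no decision hangs on the toxicity p-value. All of this stands, and it limits the size of the problem. It does not make ascertainment equal.

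The documents do not support four stronger inferences that a reader might draw:

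- *The windows differ in length.* In calendar time they are close (12 to 14 days, at most 16, against 14), and the log is scheduled for 14 days in both arms. The supportable points are that the window is undefined, that treatment days differ, and that Scrambler may end early.
- *Follow-up safety data are thrown away.* Only the 16.33 comparison omits them. They are collected (18.12), the monitoring board reviews safety data (16.7), and the suspension rule applies throughout (16.82). Restricting a device comparison to the treatment period is a legitimate choice. The rule on "Any death within 30 days of the patient's last study treatment or procedure" is a reporting requirement and shows no fault in 16.33.
- *Ascertainment alone would produce significance.* Six events against none gives p = 0.022, but this needs zero capture on TENS despite the log and calls. Six against one gives 0.098; five against none gives 0.0502.
- *Pooling Day 1 to Week 8 would cure it.* Pooling keeps the unequal first two weeks. TENS patients also keep the machine (7.211), so follow-up may include continued use.

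**Conclusion.** The point holds in limited form. Section 16.33 tests a period that is not defined in days and in which the arms are ascertained differently, and it omits the contacts that are scheduled identically. The direction of bias is unknown: closer observation would raise Scrambler counts, and more treatment days would raise TENS counts.

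Its size is also unknown, because the documents give no adverse-event rates. Under the assumed rates above, the distortion is negligible at a 10% true risk, modest at 20% unless capture is poor, and large only at high risk or with very low capture. This is a cheap improvement to a secondary goal. It does not touch the primary endpoint or the safety monitoring.

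**What to change.** 1. **Footnote 14 of Section 4.0.** Ask the same toxicity questions, in the same words, of both arms on Day 2 and once on Days 8-10: at the session for Scrambler, or by call if treatment has ended early; by call for TENS.
2. **Section 16.33, treatment period.** Define the window as Days 1-14 in both arms, state the event source and the grades counted, and base the Fisher test on the answers to those questions. List other staff-observed and log-reported events descriptively by arm. Events after the second contact and up to Day 14 would appear only in that listing, and the text should say so.
3. **Section 16.33, observation.** Show events from the weekly calls as a separate by-arm comparison over a fixed number of days from Day 1 in period 1, not pooled with Days 1-14. Eight weeks of calls after a full course end on Day 12 + 56 = 68 at the earliest and 16 + 56 = 72 at the latest, with TENS at 14 + 56 = 70. An end no later than Day 68 is therefore covered for all full courses. Note beside the table that TENS patients keep the device.

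The cost is a few extra questions at visits that already take place, an occasional call to a Scrambler patient who stopped early, one more table, and a formal test that rests on fewer reported events. No treatment changes.

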16.2 Study Design

This is a prospective randomized study to explore the efficacy of Scrambler therapy compared to TENS therapy for the treatment of chemotherapy induced peripheral neuropathy. Patients will be randomized at a 1:1 ratio to receive either scrambler therapy or TENS therapy for two weeks and will be observed for eight weeks following treatment. The primary outcome is the reduction in pain or tingling scores after 2 weeks of scrambler therapy or TENS therapy.

At the end of the eight-week observational period, patients are allowed to cross over to receive the other therapy for two weeks and will, again, be followed for an additional eight weeks. Outcomes of this second period of treatment are for exploratory purposes only. There will be no fMRI, quantitative sensory testing, or mRNA gene expression done in this second period.

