16.5 Sample size

The sample size of 50 patients (25 per arm) in this prospective randomized study is mostly determined by feasibility. This study is not designed as a confirmatory study, hence, not powered as such. The primary purpose of this study is to estimate the effect of scrambler therapy for the treatment of CIPN which will inform hypothesis formulation for future studies. If the data from this study suggest a clinically non-ignorable effect of scrambler therapy compared to TENS therapy, we will plan for a larger study to confirm its benefit. However, if the data from this trial show a very large difference in changed pain scores between the two arms, such that the primary endpoint is positive with a p-value of less than 0.05, we will interpret this outcome as evidence that Scrambler therapy is better than TENS therapy, or vice-versa, depending on which arm is doing better.

More than 45% of patients in Pachman et al.'s study experienced treatment effect (50% or more reduction in symptom scores) after 2 weeks of scrambler therapy (Pachman, Weisbrod et al. 2014). This estimate includes patients who were enrolled early in the trial who did not respond to the treatment as well as the later cohort, potentially due to the study team's inexperience in the beginning of the trial. With the current level of experience, we expect a much higher percentage of reduction in patients' symptom scores after scrambler therapy in this trial. The likelihood of detecting an improvement of 30% or more after scrambler therapy compared to TENS is high with a sample size of 25

patients per arm. Table 16.51 shows the minimum detectable improvement with at least 80% power at a one-sided .05 significance level for various plausible scenarios with 25 patients per arm.

Table 16.51. Minimum Detectable Improvement with 80% power at a one-sided 0.05 significance level

Proportion of patients achieving 50% or more reduction in symptom scores from baseline		Minimum Detectable improvement	Power (%)
TENS	Scramber		
.05	.32	.27	80
.10	.40	.30	80
.20	.54	.34	81
.30	.65	.35	81
.40	.75	.35	82

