Appendix XA Daily Scrambler Treatment Log and Adverse Event Assessment

Patient Name: _____

Date: _____

Initials	_____
Study #	_____
Date	_____
Day	_____

Pain Area #1 _____

VAS Score: Pre: _____ During: _____ Post: _____

Cable 1	Max Setting: _____	Total Treatment Time: _____ (mins)
Cable 2	Max Setting: _____	Total Treatment Time: _____ (mins)
Cable 3	Max Setting: _____	Total Treatment Time: _____ (mins)
Cable 4	Max Setting: _____	Total Treatment Time: _____ (mins)
Cable 5	Max Setting: _____	Total Treatment Time: _____ (mins)

Pain Area #2 _____

VAS Score: Pre: _____ During: _____ Post: _____

Cable 1	Max Setting: _____	Total Treatment Time: _____ (mins)
Cable 2	Max Setting: _____	Total Treatment Time: _____ (mins)
Cable 3	Max Setting: _____	Total Treatment Time: _____ (mins)
Cable 4	Max Setting: _____	Total Treatment Time: _____ (mins)
Cable 5	Max Setting: _____	Total Treatment Time: _____ (mins)

Adverse Effects Assessment: Please note any toxicities/adverse effects of treatment

Notes/Comments:

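### Hypothesis 2 predicts no substantial difference in side effects, but the only planned inference is a Fisher test of difference, which cannot support that prediction at 25 per arm

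*Combined protocol and SAP*

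**What the plan says.** Goal 2 (Section 2.2) is to assess how well Scrambler therapy is tolerated and to compare it with TENS. Hypothesis 2, under that goal, goes further. It predicts good tolerability and that "there will be no substantial differences in side effects between the Scrambler and TENS treatment groups". What counts as substantial is not defined.

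The matching analysis is in Section 16.33. The frequency and type of toxicities during therapy are to be "summarized by treatment arm and compared between arms using Fisher-exact test". The section gives no effect measure, interval, margin, significance level or sidedness.

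On size, Section 16.5 states: "The sample size of 50 patients (25 per arm) in this prospective randomized study is mostly determined by feasibility". It adds: "This study is not designed as a confirmatory study, hence, not powered as such". Table 16.51 gives the "minimum detectable improvement with at least 80% power at a one-sided .05 significance level", but for the efficacy responder endpoint only. The one rule for interpreting a p-value, "such that the primary endpoint is positive with a p-value of less than 0.05", also concerns only the primary endpoint, and it covers only a positive result.

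**The concern.** The hypothesis asserts similarity, while the planned test can only provide evidence of a difference. When Fisher is not significant, the data may be compatible with no difference, with a large one, or with both, and the p-value does not say which. Without an interval or a stated meaning for *substantial*, the plan offers no inferential basis for saying that Hypothesis 2 was supported.

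With 25 per arm this matters in practice, because non-significance is the likely outcome even when toxicity differs by 20 points. What is at stake is a report that the arms were equally well tolerated when the data could not tell.

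**Working it through.** **The plan's own figure.** The plan states no power or precision for tolerability. Its only power figures are in Table 16.51, for efficacy. With 25 per arm and one-sided 0.05, the pooled normal approximation is

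power = Φ{[d − 1.645·√(2p̄(1−p̄)/25)] / √([p₁(1−p₁)+p₂(1−p₂)]/25)},

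where d = p₂ − p₁ and p̄ is the mean of p₁ and p₂. It gives 80.7, 80.4, 81.7, 81.3 and 82.1%, against the stated 80, 80, 81, 81 and 82%. The table reproduces, but it does not bear on Section 16.33.

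**Inputs.**
- 25 per arm (Sections 16.2 and 16.5), all assumed to contribute toxicity data.
- Two-sided 0.05 is an assumption. It suits a hypothesis about differences in either direction. One-sided 0.05 is shown as a sensitivity check.
- True toxicity rates are assumptions, because the documents give none. Section 8.0 says only that substantial toxicity is not expected.

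**Observed 20-point excess (5 more patients of 25).** For 0 vs 5, the one-sided Fisher p is C(25,5)/C(50,5) = 53,130/2,118,760 = 0.0251. With equal arms the two-sided value is double, 0.0502. Other pairs:

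| Patients with toxicity | Two-sided p | One-sided p |
|---|---|---|
| 0 vs 5 | 0.0502 | 0.025 |
| 1 vs 6 | 0.098 | 0.049 |
| 2 vs 7 | 0.138 | 0.069 |
| 5 vs 10 | 0.217 | 0.108 |
| 10 vs 15 | 0.258 | 0.129 |

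Across all 21 pairs with a 5-patient gap, the smallest two-sided p is 0.0502. Two-sided significance needs a gap of 24 points at 0 vs 6 or 1 vs 7, 28 points at 2 vs 9, and 32 points from 3 vs 11 through the mid-range.

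**True 20-point excess.** The probability of non-significance is the sum of b(i; 25, p₁)·b(j; 25, p₂) over all tables (i, j) with Fisher p > 0.05, where b is the binomial probability:

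| True rates (assumed) | Non-significant, two-sided 0.05 | Non-significant, one-sided 0.05 |
|---|---|---|
| 5% vs 25% | 63% | 48% |
| 10% vs 30% | 70% | 55% |
| 20% vs 40% | 77% | 65% |

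**What an interval would show.** The Newcombe interval combines the two Wilson intervals. For 0/25 the Wilson limits are 0 and 0.133; for 5/25 they are 0.089 and 0.391.
- 5/25 vs 0/25: lower limit 0.20 − √(0.111² + 0.133²) = 0.026; upper limit 0.20 + (0.391 − 0.20) = 0.391. The interval is about 3 to 39 points, where Fisher gives p = 0.0502.
- 5/25 in each arm: ±√(0.111² + 0.191²) = ±0.22.
- 0/25 in each arm: ±0.13.
- 10/25 vs 5/25: −5 to +42 points.

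**The case against.** The strongest reply is that the plan does not make the error. A reader might infer that a non-significant Fisher result will be taken as support for Hypothesis 2, but no section says so. A reader might also infer that the goal itself is to demonstrate similarity. The goal is to evaluate and compare, and a test of difference fits *compare*. Only the hypothesis predicts similarity. Both points stand, so the defect is a missing basis for inference and not a wrong rule.

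Nor would an excess be hidden. Frequencies are tabulated by arm, so 0 vs 5 would be visible. Section 16.8 sets accrual suspension rules by arm for related events of grade 3 or higher, and Section 16.7 has the safety board review at least twice a year. These are real safeguards. However, the table carries no measure of uncertainty, and the monitoring is not a between-arm comparison.

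The arithmetic depends on assumptions. At one-sided 0.05, the level used in Table 16.51, 0 vs 5 and 1 vs 6 would be flagged. A true 20-point excess is not always missed either: two-sided Fisher detects it in 37%, 30% and 23% of trials at the three assumed rate pairs. Toxicity may also be low, since two earlier Scrambler trials described in Section 1.4 reported no adverse effects.

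A further tempting reading is that low-grade effects would be lost. Section 10.31 limits which events go on case report forms, while the daily Scrambler log asks: "Please note any toxicities/adverse effects of treatment". But Section 16.33 sets no grade limit and the daily log is a scheduled procedure, so the documents do not establish that loss.

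Finally, the trial is declared non-confirmatory. That lowers the weight of the point. It also favours an interval, because Section 16.5 gives estimation as the main purpose.

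**Conclusion.** The point holds in limited form. Beyond by-arm frequencies, Section 16.33 offers only a test of difference for a hypothesis of no substantial difference, and that test cannot support the hypothesis. At an assumed two-sided 0.05 with 25 per arm, no observed 20-point excess reaches significance. True 20-point excesses are non-significant in 63% to 77% of trials at the assumed rates, and in 48% to 65% at one-sided 0.05.

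The documents do not support saying that the trial will declare similarity from non-significance, or that an excess would go unseen. This is a worthwhile reporting correction on a secondary goal of an exploratory trial. It does not affect the primary analysis.

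**What to change.** In Section 16.33:
1. Report the risk difference, Scrambler minus TENS, in the proportion of patients with any toxicity, with a 95% Newcombe interval.
2. State that a non-significant Fisher result is not evidence of similarity.
3. Base any statement on Hypothesis 2 on that interval, or reword Hypothesis 2 as descriptive.

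This needs a few lines of text and one extra column in the toxicity table, and the sample size does not change. The price is candour. At 5/25 in each arm the interval is about ±22 points, so the trial may have to say it cannot claim similarity. At low counts the interval and Fisher can also disagree, as at 0 vs 5, so the plan should say which one is used for interpretation.

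Three further steps are not proposed:
- **A pass/fail margin.** It would turn a feasibility-sized trial into a similarity test. For equal true rates p, the power to exclude an assumed 20-point excess is Φ{0.20/√(2p(1−p)/25) − 1.96}, about 90%, 65% and 42% at p = 5%, 10% and 20%.
- **An interval for every toxicity type.** This would add many sparse comparisons.
- **Switching the source to the daily logs.** They have no grade or attribution field. Scrambler is operator-delivered and TENS is self-applied at home, so ascertainment could differ by arm.
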